Assessment of the prognostic value of nerve damage biomarkers in acute and chronic organophosphate toxicity

Study protocol

JULY 30, 2023

INTRODUCTION

Organophosphates are among the most easily accessible toxic compounds worldwide. The global occurrence of poisoning due to organophosphates is estimated to be 300,000 to 2 million cases per year, varying between accidental exposure and suicidal attempts ^(1,2). Owing to the high incidence of exposure, research focused on the detection of the possible mechanisms of toxicity, as well as evaluation of various antidote efficacy and biomarkers that can be used as mortality predictors. The main mechanism of pesticides toxicity is via inhibition of acetylcholinesterase enzyme responsible for the degradation of the neurotransmitter acetylcholine. This abrupt increase in acetylcholine levels leads to a cholinergic surge with continuous stimulation of receptors leading to the manifestation of signs and symptoms that vary according to the route of exposure to organophosphates ^(3,4). Another suggested mechanism was the oxidative stress induced by the pesticides ⁽²⁾.

However, only few studies focused on biomarkers and their quantitation. Results emphasized the importance of detecting the levels of serum cholinesterase as a prognostic indicator for acute toxicity ^(5,6). Nevertheless, it has been shown that the reliability on serum cholinesterase levels is controversial ^(2,7,8). Oxidative stress biomarkers (malondialdehyde (MDA) and total antioxidant capacity (TAC)), activity of the apoptotic biomarkers (caspase 3 and caspase 9) and pseudocholinesterase (p.ChE) were further investigated as mortality predictors ⁽²⁾. Significantly, there is paucity of evidence regarding the value of biomarkers addressing the involvement of nerve damage resulting from organophosphate poisoning in acute and chronic toxicities despite the accumulating evidence of their chronic neurological impact associated with their action on neurotoxic esterase ^(5,8)

AIM OF THE STUDY

To assess the possible prognostic value of markers of neuroinflammation and damage by a full proteomic and glycomic profile of acute and chronic organophosphate exposure patients. The profiling will be generated together with an assessment of their genotoxic effect. This will be conducted in parallel to the assessment of traditional markers of inflammation and oxidative stress.

PLAN OF THE STUDY

Study setting:

- Acute exposure patients will be recruited from the Poison Center and Emergency Department of Alexandria Main University Hospital.
- Chronic exposure patients will be recruited from farm field workers with a confirmed history of repeated occupational exposure to organophosphate pesticides.
- Control subjects will be recruited from city dwellers without any medical conditions (healthy subjects) with comparable age and gender.

Study design:

Type of the trial: cross-sectional trial

Inclusion criteria:

Chronic Patients: Adult males with age above 18.

Acute Patients: Adult males and females with age above 18 .

Controls: Adult males and females with age above 18 without previous exposure to organophosphate pesticides.

No restrictions on comorbidities in the three groups except those mentioned under Exclusion Criteria.

Exclusion criteria:

Pediatric patients, patients with neurological diseases (Parkinsonism, epilepsy, Alzheimer's disease , etc.) and any patient who does not meet the inclusion criteria.

Target population:

Patients with acute and chronic exposure to organophosphates.

Sample size: Total number between 60 to 90 patients, divided into three groups:

- 1- Controls without previous exposure to organophosphates ($n \geq 15$).
- 2- Patients with chronic exposure to pesticides ($n \geq 30$).
Patients with acute exposure to organophosphates ($n \geq 30$).

Outcome assessment:

Identification of a neuroinflammatory biomarker that correlates with nerve injury.

Type of sample and method of selection:

Convenience sample through nonprobability sampling methods

Data collection methods and tools:

1-Patient demographics and data regarding chronic patients including: 1) history of organophosphates exposure 2) compliance to safety instructions during handling of pesticides 3) medical history 4) general health status 5) cholinergic symptoms if any will be recruited through a questionnaire answered by the patients on the day of recruitment.

2-Blood sample collection with required preparations for serum extraction.

3- Laboratory analysis for some biomarkers.

4-Proteomic and glycomic analysis to identify the biomarker that correlates with nerve injury⁽⁹⁾.

Ethical consideration:

1. The researcher will seek the approval of the Ethics Committee of Faculty of Pharmacy & Alexandria University for conducting the research.

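### Farm-worker versus city-dweller recruitment coincides exactly with chronic exposure, so a chronic-versus-control difference alone cannot be attributed to organophosphates

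*Protocol*

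**What the plan says.** All of the following is in the Protocol.

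- **Study setting, chronic group:** "Chronic exposure patients will be recruited from farm field workers with a confirmed history of repeated occupational exposure to organophosphate pesticides".
- **Study setting, control group:** "Control subjects will be recruited from city dwellers without any medical conditions (healthy subjects) with comparable age and gender".
- **Inclusion criteria:** "Controls: Adult males and females with age above 18 without previous exposure to organophosphate pesticides".
- **Sample size:** at least 15 in the group described as "Controls without previous exposure to organophosphates" and at least 30 in the group described as "Patients with chronic exposure to pesticides", within an overall total of 60 to 90.
- **Study design and sampling:** "Type of the trial: cross-sectional trial", with a "Convenience sample through nonprobability sampling methods".
- **Data collection, item 1:** the chronic subjects' questionnaire covers exposure history and "compliance to safety instructions during handling of pesticides". Demographics are named, but smoking, occupation and residence are not listed as items for all groups.

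The acute group comes from a poison center and an emergency department. No group of unexposed farm workers is planned.

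**The concern.** The two groups that would show what chronic exposure does differ in two ways at once: exposure, and the population they are drawn from. Age and gender are the only characteristics the Protocol undertakes to balance. A cross-sectional convenience sample has neither a pre-exposure baseline nor random selection to offset the rest.

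The aim is a broad proteomic and glycomic profile, with genotoxicity, inflammation and oxidative-stress measures alongside. Such markers could plausibly differ between field workers and healthy city residents for reasons unrelated to organophosphates. The controls have no evident purpose other than comparison. What is at stake is that a difference between the two source populations is reported as a marker of organophosphate nerve damage.

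This follows from the recruitment rule, not from an analysis detail that a statistical analysis plan could settle later.

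**Working it through.** The Protocol states no alpha, power, effect size or SD, so there is no planned figure to reproduce. The check has a structural part and an illustrative part.

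**1. Can exposure be separated from source?**

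Inputs: 15 controls and 30 chronic subjects (the minima under Sample size). Code exposure E = 0 for controls and 1 for chronic subjects. Code source F = 0 for city dweller and 1 for farm field worker. Under Study setting, E = F for every subject.

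- The correlation of E and F is 1.0.
- The design matrix [1, E, F] has 3 columns and rank 2.

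Only the sum of the two effects can be estimated. Adding covariates or subjects from the same two sources does not change this. For contrast, a hypothetical 15 unexposed subjects from a farm source would raise the rank to 3 of 3. No such group is planned.

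**2. How often would a pure source difference be declared?**

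Assumptions: no organophosphate effect on the marker; a source difference of d SD; two-sample t-test, two-sided 5%, equal variances.

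- Degrees of freedom: 15 + 30 − 2 = 43; critical value 2.017.
- Standard error in SD units: √(1/15 + 1/30) = √0.1 = 0.316.
- Noncentrality: d / 0.316.
- Rejection rate: P(|T| > 2.017), with T noncentral t on 43 df.

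| Assumed d (SD) | Noncentrality | Rejection rate |
|---|---|---|
| 0.2 | 0.632 | 9.5% |
| 0.3 | 0.949 | 15.3% |
| 0.5 | 1.581 | 34.0% |

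The rate applies to each marker with such a difference. A larger sample raises it, because the noncentrality grows with the sample size.

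**3. What can a within-chronic analysis offer?**

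Input: n = 30 chronic subjects. By Fisher's z, the correlation detectable with 80% power at two-sided 5% is tanh[(1.960 + 0.842)/√(30 − 3)] = tanh(0.539) = 0.49. With one adjusting covariate such as age, √26 replaces √27 and the figure is about 0.50.

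Power at smaller correlations (one marker, nominal 5%):

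- r = 0.3: z = 0.3095 × √27 = 1.61; power 36%.
- r = 0.4: z = 0.4236 × √27 = 2.20; power 60%.

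With a Bonferroni correction for an assumed 100 markers, power at r = 0.49 is about 24%.

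**4. Would splitting the controls between city and local residents show a residence effect?**

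At the minimum of 15 this gives 7 versus 8. By the same noncentral-t method (13 df), power for differences of 0.2, 0.3 and 0.5 SD is 6.5%, 8.4% and 15%. About 1.57 SD is needed for 80%.

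**The case against.** **City controls are a defensible choice.** Controls must have had no organophosphate exposure, and city dwellers serve that criterion. Local residents could carry background exposure, which would pull the contrast toward the null. This stands as a reason to keep the city controls. It does not make the contrast attributable to exposure.

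**No chronic-versus-control test is written down.** The stated outcome is a biomarker that correlates with nerve injury, and no rule says a group difference will be ascribed to organophosphates. This also stands: misattribution is a risk of the design, not a stated intention. But the control group serves comparison, so the limit on what it can show is worth writing in.

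**The acute group helps in part.** It is not restricted to farm workers, so a marker shifted in both exposed groups is not explained by farm source alone. That is indirect support. Acute subjects are emergency patients set against healthy controls, so acute illness is an alternative explanation, and the aliasing in the chronic contrast remains.

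**Stronger readings a reader might infer.**

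- *That smoking, diet and other agrochemical contact are equally beyond adjustment.* The Protocol does not make these coincide with exposure. They can vary within groups and could be adjusted for where recorded and overlapping. Strict aliasing applies to recruitment source only. Rural residence of the chronic group and non-farm work among controls are close inferences, not stated facts.
- *That half the controls should be recruited locally.* At 7 versus 8 a residence effect of the assumed size would almost never be detected, and non-farming local controls would leave field work confounded with exposure.
- *That no marker should be declared without a significant exposure-response.* At n = 30 such a rule would discard most real effects of moderate size, and declaration rules commonly belong in the statistical analysis plan.

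**Conclusion.** The point holds for recruitment source. Study setting fixes it as identical to chronic exposure, so a chronic-versus-control difference taken alone cannot be attributed to organophosphates, whatever the analysis plan contains. This conclusion rests on the recruitment text and needs no numerical assumption.

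Its practical size does rest on assumption. For source differences of 0.2 to 0.5 SD in a marker unaffected by organophosphates, the nominal 5% error rate becomes roughly 9.5% to 34% per marker at the minimum group sizes. The documents do not say how large source differences are.

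The study is not invalidated and the control source need not change. Evidence within the chronic group does not depend on the city controls and can support attribution. It has limited power, however, and is not free of all confounding: years of exposure may track years of farm work and contact with other agrochemicals.

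**What to change.** 1. **Add a supportive exposure-response analysis within the chronic group.** Use exposure history and safety compliance, both already on the questionnaire, adjusted for age. Specify that history is recorded as years and frequency, since the Protocol does not say in what form it is taken. Report the estimate with its confidence interval beside each chronic-versus-control difference, not as a pass/fail condition.
2. **Ask about smoking, occupation and residence in all three groups.** Adjust for smoking and for any other factor that overlaps between groups.
3. **State the limit on interpretation in the Protocol.** A chronic-versus-control difference without exposure-response support is to be reported as a farm-worker versus city-dweller difference, not as an organophosphate effect.

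The cost is a few questionnaire items, one further analysis and more cautious conclusions. Because the exposure-response analysis is imprecise at n = 30, an interval that includes zero should not be read as showing no organophosphate effect.

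### The title and aim ask for prognostic value, but the design is cross-sectional and no outcome after sampling is recorded, so the study cannot answer its own question.

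*Protocol*

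**What the plan says.** The title is "Assessment of the prognostic value of nerve damage biomarkers in acute and chronic organophosphate toxicity". The Aim of the Study section repeats the goal: "To assess the possible prognostic value of markers of neuroinflammation and damage", by proteomic and glycomic profiling of acutely and chronically exposed patients.

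Under Study design the protocol states "Type of the trial: cross-sectional trial". Under Outcome assessment the only outcome is "Identification of a neuroinflammatory biomarker that correlates with nerve injury", with no time point.

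Data collection methods and tools lists four items:

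1. Demographics and clinical history, introduced as "Patient demographics and data regarding chronic patients including" a set of history and symptom items, which "will be recruited through a questionnaire answered by the patients on the day of recruitment".
2. "Blood sample collection with required preparations for serum extraction", stated once.
3. Laboratory biomarkers.
4. Proteomic and glycomic analysis.

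The Sample size section gives at least 15 controls, 30 chronic and 30 acute patients. The protocol mentions no follow-up visit or duration, repeat sample, discharge status, survival status or later neurological assessment.

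**The concern.** A marker has prognostic value if its level now predicts something observed later in the same patient. That requires at least one outcome recorded after the sample. The protocol names a prognostic aim and then fixes a design and a data list without such an outcome.

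The acute group is where the gap matters most. The Introduction discusses prognosis and mortality prediction mainly for acute poisoning, yet the itemised clinical content of the questionnaire is described for chronic patients. No clinical course or outcome item is listed for acute patients.

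At stake is the validity of the main conclusion. A report under this title would invite readers to treat a difference between exposed and unexposed people, or a correlation on one day, as evidence that a marker forecasts outcome. The data would not support that. If later outcomes are not captured, the loss may not be recoverable at analysis.

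**Working it through.** **Step 1. Set the question against the data.**

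| Needed for a prognostic claim | What the protocol provides |
|---|---|
| Marker at a defined baseline | One blood collection; no timing relative to exposure or admission |
| Outcome observed later | None stated |
| Follow-up period | None stated; the design is cross-sectional |
| Marker-outcome analysis within patients | The stated outcome is correlation with nerve injury, with no time point |

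The count of later outcomes is zero in all three groups. There is no prognostic figure in the plan to reproduce. The protocol states no event rate, effect size, alpha or power, and the group minima (15, 30, 30) are the only numbers available.

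**Step 2. Is this a detail for the SAP?** The Statistical analysis section promises suitable techniques to meet the objectives. A technique needs data. An SAP can choose a model for an outcome, but it cannot create an outcome that is not collected.

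**Step 3. What could be estimated if a later outcome were added in the acute group?** Inputs: n = 30, the stated minimum; true AUC A = 0.80 (assumed); number of events e (assumed). The Hanley-McNeil variance is

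SE² = [A(1 − A) + (e − 1)(A/(2 − A) − A²) + (n − e − 1)(2A²/(1 + A) − A²)] / [e(n − e)].

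With A = 0.80:

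- A(1 − A) = 0.16
- A/(2 − A) − A² = 0.6667 − 0.64 = 0.0267
- 2A²/(1 + A) − A² = 0.7111 − 0.64 = 0.0711

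For e = 5: SE² = (0.16 + 4 × 0.0267 + 24 × 0.0711)/(5 × 25) = 1.973/125 = 0.0158, so SE = 0.126 and the half-width is 1.96 × 0.126 = 0.25. The other rows follow in the same way.

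| Events of 30 | SE | 95% half-width |
|---|---|---|
| 3 | 0.160 | 0.31 |
| 5 | 0.126 | 0.25 |
| 10 | 0.094 | 0.18 |
| 15 | 0.082 | 0.16 |

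With 3 events the interval runs from 0.49 to 1.11: it includes 0.5 and passes 1. With 5 events it runs from 0.55 to 1.05. The symmetric approximation is therefore rough at low counts.

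**Step 4. Power for one marker.** This compares acute patients with and without the event (normal approximation, two-sided 0.05, n = 30, assumed standardised difference 1.0). Power is about 28%, 38%, 59% and 71% at 2, 3, 6 and 9 events, which correspond to assumed risks of 5%, 10%, 20% and 30%. At a 5% risk, the chance of no event at all is 0.95³⁰ = 0.21. None of this allows for choosing among many proteins and glycans.

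**The case against.** The strongest reply is that the outcome, the design and the data list agree with one another. Each describes a same-time association with nerve injury, which suits a cross-sectional study. On that reading the word prognostic is a loose label, the aim already softens it to possible prognostic value, and a change of wording is enough. This has force as to the remedy: rewording is a legitimate option. It does not remove the conflict, because the title carries no such softening and the qualifier supplies no outcome.

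Four further points stand in part:

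- **Mortality prediction is background.** It appears only in the Introduction's account of earlier research, so failing to collect deaths breaks no stated promise. The finding needs only the title and aim.
- **Silence is not proof.** Acute patients are recruited at a poison center and emergency department, where a hospital course may well be recorded. The exact statement is that the protocol names no later outcome and does not say that records will be used.
- **The favourable event counts are assumed.** Five, 10 and 15 events imply risks of 17%, 33% and 50%. Fewer events would give much wider intervals, and picking the best marker from a full profile would make its AUC optimistic.
- **In-hospital outcomes reflect acute severity more than nerve injury.** An acute prognostic analysis would therefore answer only part of the title, and nothing about chronic exposure.

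**Conclusion.** The concern holds, and it must be fixed. The protocol asks a prognostic question and specifies a study with no outcome after sampling. Zero prognostic outcomes means zero prognostic estimates, whatever the analysis. This part rests on the text alone and needs no numerical assumption.

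The group comparisons and same-day correlations are unaffected, but they can be reported only as association with exposure or discrimination between groups.

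The precision figures show only what an added outcome would deliver. They assume 30 acute patients, a true AUC of 0.80, one prespecified marker and invented event counts. On those assumptions the result is exploratory with 5 to 15 events and close to uninformative with 3 or fewer.

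**What to change.** Choose one of two routes and apply it throughout the protocol.

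**Route A: keep a prognostic question, in the acute group only.**

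- Describe the design as a cross-sectional comparison of three groups, with in-hospital follow-up of the acute group to discharge or death.
- Fix the marker sample at admission.
- Abstract at least in-hospital death, mechanical ventilation, ICU admission and length of stay from the hospital record.
- Name one of these as the prognostic outcome. Report its association with the admission marker as an AUC or odds ratio with a confidence interval, next to cholinesterase, and label it exploratory.
- For the chronic group, replace prognostic value with association with exposure.

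**Route B: drop the prognostic claim.** Remove the word from the title, aim and conclusions, and describe the objective as association with exposure and with nerve injury at the time of sampling.

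Route A costs a protocol amendment and chart abstraction for about 30 patients, with no extra patients. Use of the records may need ethics approval and consent coverage. Admission sampling is a new timing requirement that cannot be applied to samples already taken. Route B costs wording only. Under either route the prognostic claim for chronic exposure is given up.

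### Acute patients with earlier repeated organophosphate exposure can be counted as acute without being identified, so a marker of chronic exposure can be misattributed to acute toxicity

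*Protocol*

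**What the plan says.** Three parts of the protocol bear on this.

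- **Study setting.** The acute group comes from the hospital: "Acute exposure patients will be recruited from the Poison Center and Emergency Department of Alexandria Main University Hospital". The chronic group comes from the field: "Chronic exposure patients will be recruited from farm field workers with a confirmed history of repeated occupational exposure to organophosphate pesticides".
- **Inclusion and exclusion criteria.** The acute line is "Acute Patients: Adult males and females with age above 18" and the chronic line is "Chronic Patients: Adult males with age above 18". Only the third group carries an exposure condition: "Controls: Adult males and females with age above 18 without previous exposure to organophosphate pesticides". The exclusions are "Pediatric patients, patients with neurological diseases (Parkinsonism, epilepsy, Alzheimer's disease , etc.) and any patient who does not meet the inclusion criteria". None of these lines deals with a person who has both kinds of exposure.
- **Data collection, item 1.** The questionnaire covers "Patient demographics and data regarding chronic patients including: 1) history of organophosphates exposure", followed by safety compliance, medical history, general health and cholinergic symptoms. No other item asks acute patients about earlier exposure.

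The group minima are 15 controls, 30 chronic and 30 acute patients.

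**The concern.** The study sets out to profile nerve-damage markers in acute and in chronic exposure, and its introduction points to growing evidence of chronic neurological effects. Earlier repeated exposure may therefore move the very markers being measured. The authors treat past exposure as important enough to bar it in controls, yet leave it open in the acute group.

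A repeatedly exposed farm worker admitted with acute poisoning meets the acute criteria. If he is male, he also fits the chronic description, and no rule says how he is classified. If his history is not taken, he cannot be set aside, stratified or adjusted for later. A statistical analysis plan cannot repair this, because the variable would not exist. What is at stake is attribution: a difference between acute patients and controls could partly reflect long-standing exposure and be reported as an effect of the acute poisoning.

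**Working it through.** **Step 1: the text.**

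| Group | Condition on earlier exposure | Exposure history listed |
|---|---|---|
| Control | none allowed | not listed, but entry requires no earlier exposure |
| Chronic | confirmed repeated occupational exposure | yes |
| Acute | no condition | not listed |

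Only the acute group has neither a condition nor a listed history.

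**Step 2: inputs for an illustration.** From the protocol: group minima of 15, 30 and 30. The protocol gives no overlap rate, effect size, SD or significance level, so the following are assumptions:

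- a fraction p of acute patients also has repeated earlier exposure, with p from 10% to 50%;
- the marker responds only to chronic exposure, by c = 0.74 SD, chosen because it gives about 80% power at 30 vs 30;
- two-sided 5% t test, SD of 1 in each group.

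**Step 3: chance of any overlap.** P(at least one among 30) = 1 − (1 − p)^30. This is 78.5% at p = 5%, 95.8% at 10% and 99.9% at 20%. The expected numbers are 1.5, 3 and 6 patients.

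**Step 4: acute versus control (30 vs 15).** With no acute response, the shift is p × c. The noncentrality is p × c / √(1/30 + 1/15), with 43 degrees of freedom and critical value 2.017. At p = 20%: 0.148 / 0.316 = 0.468, so rejection is 7.4%.

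**Step 5: acute versus chronic (30 vs 30), if that comparison is made.** The difference is c × (1 − p). The noncentrality is c(1 − p) / √(2/30), with 58 degrees of freedom and critical value 2.002. At p = 20%: 0.592 / 0.258 = 2.293, so power is 62%.

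| p | Shift, acute vs control (SD) | Rejection rate | Difference, acute vs chronic (SD) | Power |
|---|---|---|---|---|
| 0% | 0 | 5.0% | 0.74 | 80% |
| 10% | 0.07 | 5.6% | 0.67 | 72% |
| 20% | 0.15 | 7.4% | 0.59 | 62% |
| 30% | 0.22 | 10.5% | 0.52 | 51% |
| 50% | 0.37 | 20.8% | 0.37 | 29% |

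**Step 6: check of the SD assumption.** A mixed acute group has an SD slightly above 1. Simulating the mixture at p = 20%, 30% and 50% gives rejection of about 7%, 10% and 19%, and power of about 60%, 48% and 28%. The picture is unchanged.

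**The case against.** **The groups are recruited in different places.** They are, and the chronic group is male only while the acute group includes both sexes. This may keep overlap low, but place and sex do not establish exposure history.

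**The overlap is unknown.** This stands. A reader might infer that the acute group is in fact contaminated. The protocol gives no rate, and the bias is zero if no acute patient has earlier exposure. At p = 10% the rejection rate is 5.6%, close to nominal. The illustration is also a worst case in assuming no acute response at all.

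**Acute versus chronic is not a named comparison.** This stands too. A reader might take it as the main contrast because both words are in the title. The aim is prognostic value in both kinds of patient, and the stated outcome is a marker that correlates with nerve injury. The power loss therefore applies only if that comparison is made.

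**The reverse case.** A reader might expect the same blind spot for chronic workers with a recent acute episode. It is largely covered, because exposure history, medical history and cholinergic symptoms are collected from chronic patients.

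**The questionnaire sentence is loose.** A wider reading could extend the list to all patients. As written, "data regarding chronic patients including: 1) history of organophosphates exposure" attaches the item to the chronic group. Even on the wider reading, no rule classifies a patient with both exposures.

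**Keeping previously exposed acute patients is a legitimate choice.** Agreed. Excluding them outright would narrow the population sampled, and the point does not require it.

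**Conclusion.** The point holds as a gap in eligibility and data collection. Acute patients with earlier repeated occupational exposure can enter the acute group and, on the natural reading, remain unidentified, so that an effect of chronic exposure can be credited to acute toxicity.

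The size cannot be fixed from the protocol. Under the stated assumptions it is negligible to small for acute versus control at 10% overlap, and material from about 30%, where rejection is roughly twice the nominal 5%. These rejections are best described as misattribution rather than chance false positives, since the group means then truly differ. The change is worth making because p is unknown and the protocol provides no clear means of learning it, and because a history not taken at enrolment may be hard or impossible to recover.

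**What to change.** 1. Extend the exposure-history part of questionnaire item 1 to acute patients, using an informant when the patient cannot answer.
2. State that a patient with both repeated occupational exposure and a current acute poisoning is classified in a separate acute-on-chronic stratum. Analyse acute versus control, and any acute-versus-chronic comparison, without that stratum or adjusted for prior exposure.
3. For chronic patients, use the exposure history already collected to flag a recent acute episode, with the look-back period stated in advance.

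The cost is one more questionnaire item for acute patients, a sentence or two on classification, and a slightly smaller group of purely acute patients. The change concerns study classification only.

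### The stated total of 60 to 90 starts 15 below the sum of the three group minima (75), so totals of 60 to 74 cannot meet the group sizes

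*Protocol*

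**What the plan says.** The only statement of planned enrolment is the Sample size entry in the Protocol, under Plan of the study. It opens: "Sample size: Total number between 60 to 90 patients, divided into three groups". Three lines follow, controls first:

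- "Controls without previous exposure to organophosphates ($n \geq 15" (a minimum of 15)
- "Patients with chronic exposure to pesticides ($n \geq 30" (a minimum of 30)
- "Patients with acute exposure to organophosphates ($n \geq 30" (a minimum of 30)

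Three other entries bear on whether controls belong in the total:

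- The inclusion criteria, after naming chronic patients, acute patients and controls, say "No restrictions on comorbidities in the three groups except those mentioned under Exclusion Criteria". Here the three groups include controls.
- The target population is given as "Patients with acute and chronic exposure to organophosphates", which leaves controls out.
- The study setting says "Control subjects will be recruited from city dwellers without any medical conditions", which calls controls subjects rather than patients.

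No other section gives a participant number or says that controls are counted separately.

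**The concern.** A total that is split into three groups cannot be smaller than the sum of the three group minima. Here the bottom of the permitted range is. A study that enrolled 60 people would meet the headline total and necessarily miss at least one group minimum.

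Participants are recruited as a convenience sample, and the protocol shows no sample size calculation behind the figures. These lines are therefore the only written target against which recruitment can be judged. The protocol states 60 as the overall minimum and implies 75. It also leaves open whether 90 is the ceiling for everyone enrolled or only for the exposed patients. An ethics committee asked to approve the study needs both figures.

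**Working it through.** **Inputs** (all from the Protocol, Sample size): total T from 60 to 90; controls at least 15; chronic exposure at least 30; acute exposure at least 30.

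**Step 1. Try to reproduce the lower bound.** The smallest total that meets all minima is the sum of the minima:

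15 + 30 + 30 = 75

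The protocol states 60, so its figure is not reproduced. The gap is 75 − 60 = 15, and 15/75 = 20%.

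**Step 2. Find which permitted totals are workable.** The combined shortfall at total T is 75 − T when T is below 75, and zero otherwise.

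| Total T | Controls left after 30 + 30 exposed | Combined shortfall |
|---|---|---|
| 60 | 0 | 15 |
| 74 | 14 | 1 |
| 75 | 15 | 0 |
| 90 | 30 | 0 (15 to spare) |

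There are 90 − 60 + 1 = 31 whole-number totals in the range. Those from 60 to 74 (15 values, 15/31 = 48%) cannot meet the minima; those from 75 to 90 (16 values) can. This count describes how much of the written range is unusable. It is not a probability that enrolment would end there.

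**Step 3. Look for a reading that gives 60.** The two exposed groups alone give 30 + 30 = 60, which matches the lower bound but omits the controls that the sentence includes. If that was the intention, the overall range with exactly 15 controls is 60 + 15 = 75 to 90 + 15 = 105. It is higher with more controls, since no ceiling for controls is given. The figures also fit three equal groups of 20 to 30 (3 × 20 = 60, 3 × 30 = 90), but those do not match the minima listed. The protocol does not say where 60 came from, so arithmetic alone cannot settle it.

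**Step 4. Compare the two main readings.**

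| Reading | Overall minimum | Overall maximum | What is wrong in the text |
|---|---|---|---|
| Total covers all three groups | 75 | 90 | The lower bound of 60 |
| Total covers exposed patients only | 75 (60 + 15) | 105 with exactly 15 controls | The three-group wording; overall total not stated |

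If the minima are binding, both readings put the true overall floor at 75. They differ at the ceiling. Under neither is the sentence correct as it stands.

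**The case against.** The strongest reply is that the lines are not in full conflict. Every total from 75 to 90 satisfies all of them, and a reader who treats the minima as binding will take 75 as the working floor and 90 as the ceiling. On this view 60 is merely a slack bound. That is right as far as it goes, and the group targets are clear. But it rescues the entry only by disregarding a bound that the protocol states.

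It can also be said that the exposed-only reading is conjecture. The sentence itself splits the total across three groups with controls first, and the exclusion criteria use the word patient in a general way, so the count in patients proves little. A target population describes whom the study is about, not who is counted. This also stands in part: the plain wording favours a three-group total. The exposed-only reading remains a possibility, not a finding, and the range of 75 to 105 depends on it.

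Finally, nothing shows that recruitment would stop below 75, no power consequence can be derived, and the repair is small. All true. These points limit the consequence; they do not make the figure correct. Nor could a separate statistical analysis plan make this protocol sentence consistent, because the problem is a disagreement between figures the protocol states, not a missing method.

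**Conclusion.** The concern holds: the Sample size entry is wrong as written. Its lower bound is 15 participants below the sum of its own group minima, and totals of 60 to 74 are incompatible with those minima. The upper bound of 90 is consistent on the three-group reading.

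This rests on two things the text supports: that the minima are meant as requirements, and that controls are one of the three groups into which the total is split. If the second was not the sponsor's intention, the error moves from the number to the wording, and the overall total is then missing. No claim is made about power or precision, because the protocol gives no effect size, variability, significance level or power. The error is definite and lies in a core design figure, so it should be corrected, but it does not undermine the design.

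**What to change.** Restate the entry so that total and minima agree. The sponsor should choose according to what was meant:

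- **Controls included, minima kept:** *Total 75 to 90 participants: at least 15 controls, at least 30 with chronic exposure and at least 30 with acute exposure; each group minimum is to be met whatever the total.*
- **Range meant for exposed patients only:** *60 to 90 exposed patients, at least 30 chronic and at least 30 acute, plus at least 15 controls*, followed by the overall total including controls.

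Lowering one or more group minima would also restore consistency, but that changes the planned group sizes rather than correcting a sentence, and would need its own justification.

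Either of the two wordings costs one sentence and requires no enrolment beyond the minima already stated. On the second, the overall total on paper would exceed 90 at its upper end (105 with exactly 15 controls), and approval documents should show that figure.
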